9.2.2.3 Visit 4 (Day 14 ± 3 days)

New text:

9.2.2.3 Visit 4 (Day 14 ± 1 days)

Visit 10 (Day 420 ± 7), Section 9.2.3.2

Old text:

- Assessment of Chagas' disease signs and symptoms (to be performed during physical examinations); see Section 9.4.4
- Concentration test for *T. Cruzi* (subjects < 8 months of age), conventional and nonconventional serologic testing for Chagas' disease and qPCR
- Assessment of AEs
- Concomitant medications

• • •

New text:

- Assessment of Chagas' disease signs and symptoms (to be performed during physical examinations); see Section 9.4.4
- 12-lead ECG (optional in subjects < 5 years of age at the discretion of the investigator)
- Conventional and non-conventional serologic testing for Chagas' disease and qPCR
- Assessment of AEs
- Concomitant medications

•••

9.3.2.2 Visit 11 (Day 420 ± 7)

Old text:

- Assessment of Chagas' disease signs and symptoms (to be performed during physical examinations); see Section 9.4.4
- Conventional and non-conventional serologic testing for Chagas' disease and qPCR
- Assessment of AEs

	Integrated Clinical Study Protocol		
	BAY A2502/ 16027		
03 NOV 2020	Version 11.0	Page:	187 of 259

New text:

- Assessment of Chagas' disease signs and symptoms (to be performed during physical examinations); see Section 9.4.4
- 12-lead ECG (optional in subjects < 5 years of age at the discretion of the investigator)
- Conventional and non-conventional serologic testing for Chagas' disease and qPCR
- Assessment of AEs

• • •

Efficacy, Section 9.4

Old text:

Efficacy assessments will be obtained at designated study visits (see Table 9–1). The primary efficacy variable will be sero-reduction or sero-conversion at 12 months post-treatment using two conventional ELISA serology tests as the measure of efficacy.

A quality control program will be implemented for the primary efficacy variable (i.e., ELISA concentration). At least 20% of measurements, chosen at random, will be confirmed by a reference laboratory (Chagas Service, Buenos Aires Children's Hospital "Ricardo Gutierrez").

Other efficacy variables include disease state determined by qPCR, concentration tests for *T. cruzi* (subjects < 8 months of age at randomization), conventional and non-conventional serologic testing, and clinical signs/symptoms of Chagas' disease.

. . .

New text:

Efficacy assessments will be obtained at designated study visits (see Table 9–1). The primary efficacy variable will be sero-reduction or sero-conversion at 12 months post-treatment using two conventional ELISA serology tests as the measure of efficacy.

A quality control program will be implemented for all tests according to the laboratory QC/QA department SOPs.

Other efficacy variables include disease state determined by qPCR, concentration tests for *T. cruzi* (subjects < 8 months of age at randomization), conventional and non-conventional serologic testing, and clinical signs/symptoms of Chagas' disease.

• • •

Polymerase chain reaction test, Section 9.4.1

Old text:

A qPCR test will be performed at the Screening Visit, Visits 3, 6, and 8, and Follow-up Visits 10 and 11.

Details describing the collection, processing, storage and shipment of qPCR blood samples, and the qPCR test protocol, are described in Section 1.

New text:

	Integrated Clinical Study Protocol		
	BAY A2502/ 16027		
03 NOV 2020	Version 11.0	Page:	188 of 259

A qPCR test will be performed at the Screening Visit, Visits 3, 6, and 8, and Follow-up Visits 10 and 11.

Details describing a suggested collection, processing, storage and shipment for qPCR blood samples, and a suggested qPCR test protocol, are described in Section 1. The study central laboratory procedures and qPCR protocol will be followed.

Serological tests, Section 9.4.2

Old text:

•••

All subjects ≥ 8 months to < 18 years of age at randomization will have two baseline specimens collected for serologic testing. One sample will be used to determine the initial diagnosis of Chagas' disease while the other sample will be frozen and retained to be assayed along with the 12-month post-treatment specimen as an internal control. Subjects < 8 months of age at randomization will have one specimen obtained which will be frozen and retained. Total blood volume to be taken for the required for three serological and PCR tests is 4.05.0 mL, depending on the subject's age. Care will be taken to minimize sample volumes by using a micro-sampling collection technique.

Details describing the collection, processing, storage and shipment of blood samples, and the serologic test protocol, will be described in a separate serologic test manual. Initial serologic tests will be performed by a local laboratory according to the standard of care for each country. Subsequent tests will be performed by a central laboratory.

...

New text:

•••

All subjects ≥ 8 months to < 18 years of age at randomization will have two baseline specimens collected for serologic testing. One sample will be used to determine the initial diagnosis of Chagas' disease while the other sample will be frozen and retained to be assayed later as an internal control. Subjects < 8 months of age at randomization will have one specimen obtained which will be frozen and retained. Total blood volume to be taken for the required three serological and PCR tests is 4.05.0 mL, depending on the subject's age. Care will be taken to minimize sample volumes by using a micro-sampling collection technique, when possible.

Details describing the collection, processing, storage and shipment of blood samples, and the serologic test protocols, will be described in a separate serologic test manual from the central laboratory.

•••

Statistical methods and determination of sample size, Section 10

General considerations, Section 10.1

Old text:

	Integrated Clinical Study Protocol	
	BAY A2502/ 16027	
03 NOV 2020	Version 11.0	Page: 189 of 259

This study has been designed to focus on the efficacy and safety of treatment with nifurtimox in children diagnosed with Chagas' disease. In this study, approximately 390 pediatric subjects will be randomized to ensure 330 evaluable pediatric subjects (2:1 randomization, 60-day regimen vs. 30-day regimen). A subject is considered evaluable if there is sufficient information to determine whether or not he or she is cured. Subjects will be stratified by age into four-cohorts. Enrollment will continue until there are a total of at least 330 evaluable subjects. A minimum of 38 subjects in each age stratum is targeted, as this would include an expected 25 subjects randomized to the 60-day dosing regimen. This is nearly 10% of the study sample size, and should provide a maximum CI half-width of approximately 0.20. Enrollment will continue until this specification is met, unless it is determined that such a target would be unlikely to be reached in a reasonable time.

• • •

New text:

This study has been designed to focus on the efficacy and safety of treatment with nifurtimox in children diagnosed with Chagas' disease. In this study, approximately 390 pediatric subjects will be randomized (2:1 randomization, 60-day regimen vs. 30-day regimen). Subjects will be stratified by age into four strata. A minimum of 38 subjects in each age stratum is targeted, but not required, in order to be able to derive meaningful safety conclusions. Enrollment will continue until this specification is met, unless it is determined that such a target would be unlikely to be reached in a reasonable time.

• • •

10.2 Analysis sets

Old text:

The primary efficacy analysis will be done using the full analysis set (FAS), which is the set of subjects who received at least one dose of study drug. This set is sometimes referred to as the modified intent to treat set. Analyses will also be done using the per-protocol set, which is comprised of subjects treated with study drug who have no major protocol deviations. Complete specifications will be provided in the SAP.

Analyses of safety and background data will be performed on the FAS.

New text:

The primary efficacy analysis will be done using the full analysis set (FAS), which is the set of subjects who received at least one dose of study drug. Analyses will also be done using the per-protocol set, which is comprised of subjects treated with study drug who have no major protocol deviations. Complete specifications will be provided in the SAP.

Analyses of safety and background data will be performed on the FAS.

Variables and planned statistical analyses, Section 10.3

Old text:

Variables

	Integrated Clinical Study Protocol	
	BAY A2502/ 16027	
03 NOV 2020	Version 11.0	Page: 190 of 259

The primary efficacy variable will be sero-reduction or sero-conversion at 12 months posttreatment using two conventional ELISA serology tests as the measure of efficacy. This sero-reduction or sero-conversion is considered cure, and the primary variable is binary (cure, no cure). In the event of discordancy between the two conventional ELISA test results for subjects \geq 8 months of age, the average percentage sero-reduction will be used (e.g., Test #1 = 15% and Test #2 = 25%; average = 20% and, hence, cure). The methodology for calculating the average percentage sero-reduction will be specified in the SAP.

Secondary efficacy variables include clinical signs/symptoms of Chagas' disease, concentration test for *T. cruzi* (subjects < 8 months of age at randomization), conventional and nonconventional serologic testing, and disease state determined by qPCR.

...

New text:

Variables

The primary efficacy variable will be sero-reduction or sero-conversion at 12 months posttreatment using two conventional ELISA serology tests as the measure of efficacy. This sero-reduction or sero-conversion is considered cure, and the primary variable is binary (cure, no cure).

In the event of discordancy between the two conventional ELISA test results, the following will be considered:

- For sero-reduction, the average percentage of OD reductions will be used (e.g., Test #1 = 15% and Test #2 = 25%; average = 20% and, hence, cure).
- For sero-conversion, only when both test results are negative the subject is considered as negative (cure).

Secondary efficacy variables include clinical signs/symptoms of Chagas' disease, concentration test for *T. cruzi* (subjects < 8 months of age at randomization), conventional and nonconventional serologic testing, and disease state determined by qPCR.

• • •

Old text:

Statistical and analytical plans

• • •

Sero-conversion for the historical control will be estimated from cure rates as presented in two publications .[15][16 The sero-conversion rates used for placebo and benznidazole are 16% and 45%, respectively. The placebo value was derived by using a number greater than the larger of the upper limits of the 95% CIs from the two studies. Further details about the derivation of these rates will be given in the SAP.

Secondary efficacy analyses

	Integrated Clinical Study Protocol	
	BAY A2502/ 16027	
03 NOV 2020	Version 11.0	Page: 191 of 259

The same CI for the primary endpoint analysis will also be used for comparison with the historical benznidazole subjects with sero-conversion to assess whether or not their cure rates are comparable. Further details about the comparison will be given in the SAP.

A secondary analysis will be done to compare the proportion of subjects with seroreduction or sero-conversion for the 60-day and 30-day nifurtimox regimens. This will be performed using a standard, symmetric, asymptotic 2-sided 95% CI for the difference of two independent proportions.

New text:

Statistical and analytical plans

. . .

Sero-conversion for the historical placebo control is estimated as 16% from cure rates presented in two publications [15][16], taking a number greater than the larger of the upper limits of the 95% CIs from the two studies. Further details about the derivation of these rates are provided in Section10.4.

Secondary efficacy analyses

A secondary analysis will be done to compare the proportion of subjects with seroreduction or sero-conversion for the 60-day and 30-day nifurtimox regimens. This will be performed using a 2-sided 95% CI for the difference of two independent proportions.

•••

Safety

Old text:

Safety variables will be summarized by means of descriptive statistics and/or frequency tables as appropriate. Summaries will be given by treatment regimen. All post-treatment AEs and hematological/biochemical toxicities based on laboratory measurements, as well as drug-related AEs and SAEs, will be summarized by category and worst grade. AEs occurring between the time of consent and the first dose of study drug will be summarized separately. Subjects experiencing urine discoloration from riboflavin ingestion will be summarized also, although these incidences will not necessarily be considered AEs.

New text:

Safety variables will be summarized by means of descriptive statistics and/or frequency tables as appropriate. Summaries will be given by treatment regimen. All post-treatment AEs and SAEs, as well as drugrelated AEs and SAEs, will be summarized by category. AEs occurring between the time of consent and the first dose of study drug will be summarized separately. Subjects experiencing urine discoloration from riboflavin ingestion will be summarized also, although these incidences will not necessarily be considered AEs.

Missing data/drop outs

Old text:

	Integrated Clinical Study Protocol BAY A2502/ 16027	
02 11011 2020		
03 NOV 2020	Version 11.0	Page: 192 of 259

No imputations will be made for missing data due to dropouts or other causes. For the primary efficacy analysis done on the FAS, a patient without an assessment at the primary 12 month time point will be considered a treatment failure. For the secondary analysis using the PPS, patients who do not have serology determinations to assess the primary endpoint will be excluded from the analysis.

Sensitivity analyses will be performed, treating only missing values due to the following reasons as treatment failures:

1. the reason for discontinuation is known or suspected to be treatment ineffectiveness or an \mbox{AE}

2. a subject has not had a negative serology at any visit and has no serology determination for the primary analysis visit

3. an indeterminate or incorrectly performed serology determination occurs at the primary analysis visit.

. . .

New text:

No imputations will be made for missing data due to dropouts or other causes. For the primary efficacy analysis done on the FAS, a patient without an assessment at the primary 12 month time point will be considered a treatment failure. For the secondary analysis using the PPS, patients who do not have serology determinations to assess the primary endpoint will be excluded from the analysis.

The following sensitivity analyses for the primary efficacy variable will be performed:

• Missing values due to the following reasons treated as treatment failures and other missing values excluded from analysis:

1. the reason for discontinuation is known or suspected to be treatment ineffectiveness or an \mbox{AE}

2. a subject has not had a negative serology at any visit and has no serology determination for the primary analysis visit

3. an indeterminate or incorrectly performed serology determination occurs at the primary analysis visit.

- Observed data only.
- Analysis on PPS.

Synopsis and Determination of sample size, Section 10.4

Old text:

Sample size is based on the primary endpoint, the difference in the proportion of nifurtimox subjects with sero-reduction or seroconversion (60-day regimen) and the proportion of historical placebo subjects with sero-conversion. The test of superiority over placebo will be

	Integrated Clinical Study Protocol BAY A2502/ 16027	
03 NOV 2020	Version 11.0	Page: 193 of 259

powered based on the detection of a difference in proportion of 0.10. This quantity represents a difference between rates, such as 0.60-0.50=0.10, rather than the difference that would result from subtracting 10% of 0.60 (that is, 0.06) from 0.60. Given that the nifurtimox (60day) proportion of subjects with sero-reduction or sero-conversion is 0.60, 220 evaluable subjects in this group will provide at least 80% power for an exact binomial test. This sample size will provide an exact 95% CI with a width of ≤ 0.15 (e.g., [0.53,0.67]) for use in comparing nifurtimox to the proportion of historical benznidazole subjects with seroconversion.

The number of subjects in the 30-day treatment regimen is based on the width of a 95% asymptotic symmetric CI for the difference of two proportions. A sample size of 110 subjects for the 30-day subjects together with 220 subjects for the 60-day subjects will produce a CI with a half-width of approximately 0.20.

•••

New text:

This study uses historical controls estimated from cure rates presented in two publications [15][16]. The historical cure rates are as follows.

Publication	Age range	Sero-conversion rate (95%CI) in placebo patients
Andrade et al 1996	7-12	3/65 = 5% (1%,13%)
Sosa et al 1998	6 -12	2/44= 5% (1%,16%)

For the primary objective, superiority over placebo will be confirmed if the lower limit of the 95% CI for the nifurtimox (60day regimen) cure rate is greater than 16%, the larger of the upper limits of the 95% CIs from the two publications.

According to Guhl et al [31], nifurtimox 12 month post treatment cure rate is about 55%, with a sample size of 260 for the 60-day regimen, the power is 99% for the lower limit of the 95% CI to be greater than 16%.

The number of subjects in the 30-day treatment regimen is based on the width of a 95% CI for the difference of two proportions. A sample size of 130 subjects for the 30-day subjects together with 260 subjects for the 60-day subjects will produce a CI with a half-width of approximately 0.20.

•••

Data recording, Section 11.1

Old text:

• • •

	Integrated Clinical Study Protocol BAY A2502/16027	
03 NOV 2020	Version 11.0	Page: 194 of 259

For subjects consenting to undergo PK blood sampling, blood samples will be sent to the sponsor, and the data will be entered into the SAS after database lock. The following will be documented in the eCRF: Times of the two most recent medication intake prior to the visit, administered dose and exact time of dosing at the visit, exact time of blood sampling, time of first dose after blood sampling, samples sampled within time window.

New text:

...

For subjects consenting to undergo PK blood sampling, blood samples will be sent to the sponsor, and the data will be entered into the SAS after database lock.

Administered dose and exact times of two medication intakes during the visit, exact times of blood sampling, time of first dose after blood sampling, and samples collected within time window will be recorded in the eCRF.

Reference list, Section 14

The following references were added to the reference list per changes made as a result of Amendment 2, and the cross-references were renumbered in the list and within the protocol body accordingly.

28. First Chagas Paltform Technical Meeting Report, September 1, 2009, Rio de Janeiro


Subject diary, Appendix 16.3

The subject diary was updated.

15.3 Amendment 3

There have been 3 global amendments to the study protocol. Changes made to the study protocol by Amendment 1 are described in detail in Section 15.1, by Amendment 2 in Section 15.2 and by Amendment 3 in Section 15.3.

	Integrated Clinical Study Protocol BAY A2502/16027		
03 NOV 2020	Version 11.0	Page:	195 of 259

15.3.1 Overview of changes

This section provides a conceptual overview of all modifications to the amended protocol, as introduced by this amendment. The reason for the protocol change included in Amendment 3 is to delete a phrase "and ECG abnormalities" which was added in error to amendment 2.

The associated changes to the protocol text are detailed in Section 15.3.2.

Sections affected include:

• Adverse events of special safety interest, Section 9.6.1.6

15.3.2 Changes to the protocol text

In this section, deletions are erossed out, while additions are underlined.

Section 9.6.1.6: Adverse events of special safety interest

Old text:

In this study, all AEs of weight loss of > 20%, severe rash, severe polyneuropathy, and ECG abnormalities²⁰⁸ will be considered AEs of special safety interest. Adverse events of special safety interest will be assessed, monitored, and reported as described in Section 9.6.1.4

New text:

In this study, all AEs of weight loss of > 20%, severe rash and severe polyneuropathy will be considered AEs of special safety interest. Adverse events of special safety interest will be assessed, monitored, and reported as described in Section 9.6.1.4

15.4 Amendment 4

There have been 4 global amendments to the study protocol. Changes made to the study protocol by Amendment 1 are described in detail in Section 15.1, by Amendment 2 in Section 15.2, by Amendment 3 in Section 15.3 and by Amendment 4 in Section 15.4.

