6.3.1 Withdrawal

Withdrawal criteria

Subjects *must* be withdrawn from the study if any of the following occurs:

• At their own request or at the request of their parents' or legally acceptable representative. At any time during the study and without giving reasons, a subject may

	Integrated Clinical Study Protocol	
	BAY A2502 / 16027	
03 NOV 2020	Version 11.0	Page: 40 of 259

decline to participate further. The subject will not suffer any disadvantage as a result of this decision.

- Pregnancy. If any urine pregnancy test is positive, a serum pregnancy test must be performed to confirm the result. See Section 9.6.2.⁹⁴ (not applicable to part 2)
- Subjects, with positive parasitology test at the 30-day visit for whom (1) it has been determined that the drug was administered correctly and (2) the daily dosage given was correct, must be discontinued from the study and treated with an alternative trypanocidal medication, selected by the investigator.⁹⁵ (not applicable to part 2)

Subjects *may* be withdrawn from the study if any of the following occurs:

- If, in the investigator's opinion, continuation of the study would be harmful to the subject's well-being
- At the specific request of the sponsor and in liaison with the investigator (e.g., obvious non-compliance, safety concerns)
- For the following situations that are regarded by the investigator to be related to the use of study drug (nifurtimox) (not applicable to part 2):
 - Severe nervous system disorders such as seizure, vertigo/dizziness, polyneuropathy, or peripheral neuropathy
 - Severe gastrointestinal disorders, severe decreased appetite
 - Significant loss of body weight in the judgment of the investigator
 - Severe hepatic impairment
 - Severe renal impairment
 - Psychic disorders such as disorientation, psychotic behavior
 - Development of malignant disease
 - Hematological abnormalities such as severe leukopenia

Depending on the time point of withdrawal, a withdrawn subject is referred to as either "screening failure" or "dropout" as specified below:

Screening failure

A subject who, for any reason (e.g., failure to satisfy the selection criteria), terminates the study before the time point used for the definition of "dropout" (see below) is regarded as a "screening failure."

Re-starting the defined set of screening procedures to enable the "screening failure" subject's participation at a later time point is allowed only in the following situations (not applicable to part 2):

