9.6.1.6 Adverse events of special safety interest

In this study, all AEs of weight loss of > 20%, severe rash, and severe polyneuropathy will be considered AEs of special safety interest.¹⁶⁸ Adverse events of special safety interest will be assessed, monitored, and reported as described in Section 9.6.1.4.

¹⁶⁷ Revised since Investigators' Brochure became available to serve as the reference document for nifurtimox (Amendment 1)

03 NOV 2020 Version 11.0

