## 4.3 Handling of Missing Data

#### Part 1 (CHICO)

No imputations will be made for missing values occurring in the safety and background variables. Background variables include demographics (sex, age), height/length, weight, medical/surgical history, and medication history.

All efforts will be taken to collect all data. However, despite best efforts, it may be inevitable that missing data are reported. In the primary efficacy analysis done on the full analysis set (FAS), subjects who have missing conventional serology results at the 12 month time point will be treated as failures (i.e. no cure).

For the secondary analysis using the per-protocol set (PPS), all subjects who do not have both conventional serology determinations to assess the 12-month time point will be excluded from the analysis.

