## **Adverse Events**

All adverse events occurring during the study (i.e., from signing of informed consent until last visit) will be reported. The MedDRA coding system will be used to code the adverse events.

An overview of frequencies of subjects who died, experienced any adverse event, experienced any drug-related adverse event, experienced a serious adverse event (SAE), experienced a drug-related serious adverse event, or discontinued due to an adverse event will be summarized by treatment regimen.

Adverse events will be considered treatment emergent, if they first occurred or worsened at or after first application of study medication during the course of the study up to and including 7 days after last application of study medication.

Incidence of treatment emergent AEs (TEAEs), drug-related TEAEs, serious TEAEs, drugrelated serious TEAEs, as well as TEAEs leading to discontinuation will be summarized by primary system organ class and high level term by treatment regimen.

The definitions of incidence are as follows:

- Incidence of all events: # of subjects reporting the event with a start date during or after treatment/# of subjects valid for safety.
- Incidence of drug-related events: # of subjects reporting a drug-related event with a start date during or after treatment/# of subjects valid for safety.
- Incidence of events by maximum intensity: # of subjects reporting the event at the indicated intensity with a start date during or after treatment/# of subjects valid for safety.

Adverse events leading to death, premature discontinuation and serious adverse events will be listed. In this study, all AEs of urticarial, weight loss of > 20%, severe rash, and severe polyneuropathy will be considered AEs of special safety interest. Adverse events of special safety interest will be summarized by treatment regimen.

AEs occurring between the time of consent and the first dose of study drug will be summarized separately.

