## **ECG and Vital Signs Data**

Quantitative ECG data, both original values and change from baseline, will be summarized by visit and treatment regimen. ECG interpretations will also be summarized by visit and treatment regimen. ECG data will be analyzed for the FAS and by age stratum.

Vital signs data will be analyzed descriptively. The original values and changes from baseline will be summarized by visit and treatment regimen.

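### Weight is measured throughout Part 1, but no growth-adjusted measure is planned, and the one numeric criterion for weight change (loss above 20%) cannot flag an infant who fails to gain

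*Protocol*

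**What the plan says.** **Criterion.** Protocol Section 9.6.1.6, as set by Amendment 3 (Section 15.3.2), states that "all AEs of weight loss of > 20%, severe rash and severe polyneuropathy will be considered AEs of special safety interest" and sends them through the reporting route of Section 9.6.1.4. SAP Section 6.3 (Adverse Events) has "all AEs of urticarial, weight loss of > 20%, severe rash, and severe polyneuropathy will be considered AEs of special safety interest". Neither text says which weight the loss is measured from.

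**Collection.** Protocol Table 9-1 puts weight and height/length in its safety block, in one row with vital signs, at Visits 1, 2, 3, 6, 8, 9, 10 and 11. Table 9-2 has them at the annual Part 2 visits.

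**Other references to weight.** The Part 1 phone form (Protocol Section 16.1.1; Days 14, 21 and 42) asks about any weight loss and, if there is some, the current weight. Protocol Section 6.3.1 lists "Significant loss of body weight in the judgment of the investigator" and "Severe gastrointestinal disorders, severe decreased appetite" among the drug-related situations in which a child may be withdrawn.

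**Analysis.** SAP Section 4.1 promises descriptive statistics for every collected variable at each assessment, by age stratum and regimen. SAP Section 4.3, in its rule on missing values, says: "Background variables include demographics (sex, age), height/length, weight, medical/surgical history, and medication history". Protocol Section 10.3.1.1 classes weight the same way. The safety-variable lists in SAP Section 6.3 do not mention weight or growth for either part. For vital signs SAP Section 6.3 says "The original values and changes from baseline will be summarized by visit and treatment regimen". Protocol Section 9.6.3.4 treats weight next to vital signs, but its list of vital signs is blood pressure, heart rate, respiratory rate and temperature.

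**The concern.** An infant should gain weight over a 60-day course. A criterion written as loss asks whether the child is lighter than before, not whether the child is lighter than it ought to be. Those questions nearly coincide for a 17-year-old and are far apart for a newborn. The other items specific to weight, on the phone form and in the withdrawal list, are also written as loss, so an infant whose weight stalls meets none of them.

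The Protocol's benefit-risk text lists anorexia, nausea and vomiting among the drug's effects in adults, and it names severe decreased appetite as a possible reason for withdrawal. It also targets at least 38 children per age stratum so that safety conclusions are meaningful. What is at stake is whether the weight data can support such a conclusion in the two youngest strata (0 to 27 days, and 28 days to under 8 months), or only show that nobody lost more than a fifth of body weight.

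**Working it through.** The 20% is a chosen cut-off. No sample size, power or error rate depends on it, so there is no figure of the plan to reproduce. The check asks what the cut-off means against expected weight.

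**Inputs**
- Starting weight 4 kg (full-term neonate) and 15 kg (3 years): Protocol Table 9-5. These are example weights in a blood-volume table, not growth data.
- Course length: 60 days.
- Expected proportional gain over 60 days, g: not in the documents. Assumed range 5% to 50%, with one value derived from Table 9-5.

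**Expected gain from Table 9-5, straight line**
(15 − 4) kg ÷ (36 × 30.4 days) × 60 days = 0.60 kg, and 0.603 ÷ 4 = 15.1%.

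**Formulas**
- Shortfall from expected weight with no gain: 1 − 1/(1 + g). Recorded loss: 0%.
- Shortfall at exactly 20% loss: 1 − 0.8/(1 + g).

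With g = 15.1%, expected weight is 4.60 kg. No gain leaves 4 kg, and 1 − 4/4.603 = 13.1%. A 20% loss leaves 3.2 kg, and 1 − 3.2/4.603 = 30.5%.

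| Expected gain g | Below expected, no gain (0% loss) | Below expected, at 20% loss |
|---|---|---|
| 5% (assumed) | 4.8% | 23.8% |
| 10% (assumed) | 9.1% | 27.3% |
| 15.1% (Table 9-5) | 13.1% | 30.5% |
| 20% (assumed) | 16.7% | 33.3% |
| 30% (assumed) | 23.1% | 38.5% |
| 50% (assumed) | 33.3% | 46.7% |

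The size depends on g. The direction does not: for any g above zero, a child with no gain is below expected weight and scores no loss.

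**Whether the planned summaries fill the gap**
1. SAP Section 4.1 gives mean and spread in kilograms per stratum, regimen and visit. Stratum 2 runs from 28 days to under 8 months and stratum 4 from 2 to under 18 years, so much of that spread is age. At the 38-child target and 2:1 allocation, a stratum has about 38 × 2/3 = 25 against 13 children.
2. Change from baseline is specified for laboratory, ECG and vital-sign data. Whether vital signs includes weight is left open.
3. Both regimens give active nifurtimox on Days 1 to 30 (Protocol Section 5.1), and no arm is untreated. Agreement between regimens up to Day 30 therefore says nothing about an effect of the drug on growth in that period, in any unit. Only an outside reference for expected weight can.

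**The case against.** Several readings go further than the documents allow.

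- *Weight safety rests only on the 20% rule, and poor growth would go unseen.* This is not so. The special-interest list governs reporting; it does not filter what is recorded. All Part 1 adverse events are recorded whatever their size (Protocol Section 9.6.1.3), abnormal findings on examination after screening become adverse events (Section 9.6.3.3), and a monitoring committee reviews Part 1 safety data. Serial weights exist and will be summarised by stratum, so an outright stall in mean weight in the youngest stratum could be seen. What remains is that nothing prespecified looks for it, and partial faltering in raw kilograms has no yardstick.
- *Growth failure is the main safety signal in infants.* This is unsupported. The Protocol reports anorexia in adults and describes reactions in children as generally milder and less common.
- *The criterion is loss from baseline.* The text gives no reference weight, and the general baseline rule in SAP Section 4.5 is not tied to it.
- *Age-driven growth biases the 60- versus 30-day contrast.* Randomisation is stratified by age, so expected growth is balanced between regimens apart from chance. Raw kilograms make the contrast noisier, not biased.

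It is also fair that weight sits in the safety block of Table 9-1, so calling it merely a background variable is selective. The SAP should settle which it is.

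**Conclusion.** The narrow point stands. Weight is well collected, but the only numeric criterion for weight change is a loss above 20% at every age with no reference weight, weight is not named among the SAP's safety variables, and no age-appropriate measure is specified. A newborn with no gain over 60 days would be about 13% below expected weight on the Table 9-5 interpolation, and 4.8% to 33.3% below over the assumed range, while registering no loss. That size rests on an interpolation and an assumed range; the failure to flag rests on neither. No figure in the documents is shown to be wrong, and nothing here shows that the drug impairs growth. This is an inexpensive improvement to a descriptive safety analysis, not a flaw in the trial's efficacy conclusions.

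**What to change.** Leave the special-interest definition unchanged. In SAP Section 6.3:

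1. Name weight as a safety variable.
2. Add a descriptive table of age- and sex-standardised weight z-scores: value, and change from Visit 2, at Visits 6, 8, 9, 10 and 11, by regimen and age stratum. Name the published growth standard used, and state which applies at which ages if one does not validly cover the whole range.
3. Optionally, add a descriptive 60- versus 30-day difference at Day 60 and a tabulation of falls in z-score. Neither is essential, because Part 1 safety is declared descriptive without formal testing.

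Date of birth, sex and serial weights are already collected. A growth standard is not an untreated infected control, so change within the child is the more useful column. If the Part 1 tables have already been run, label this one supplementary.

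Two inconsistencies need reconciling. Table 9-1 schedules weight at Visit 6, but the Visit 6 description (Protocol Section 9.2.2.5) omits it. The special-interest lists in Protocol Section 9.6.1.6 and SAP Section 6.3 also differ by the urticarial entry.

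Cost: SAP wording and one more descriptive safety table, with no new data.
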